5.2. Determination of Sample Size

Approximately 32 at least mildly active RA subjects will be enrolled and randomly assigned in a 1:1:1:1 ratio to 1 of the 3 doses of LY3337641 (5, 10, or 30 mg) or placebo in Part A. This sample size is customary for evaluating safety and PK and/or PD parameters, and is not powered on the basis of statistical hypothesis testing.

Approximately 244 moderately to severely active RA subjects will be enrolled and randomly assigned in a 1:1:1:1 ratio to 1 of the 3 doses of LY3337641 (5, 10, or 30 mg) or placebo in Part B. All subjects who discontinue the treatment early (before Week 12) will be considered as failing the primary endpoint in Part B. The sample size of 61 subjects per arm will provide at least 80% power at the 2-sided .05 significance level to detect a difference of 25% in the primary endpoint (ACR20 response rate at Week 12) between each LY3337641 dose and placebo, assuming a 30% placebo response rate.

If the assessment committee determines that a dose adjustment is needed, the total study sample size may be adjusted.

5.3. Method of Treatment Assignment

For Part A, subjects who meet all criteria for enrollment will be randomly assigned in a 1:1:1:1 ratio to 1 of the 4 study arms at Visit 2 in a double-blind fashion. For Part B, subjects who meet all criteria for enrollment will be randomly assigned in a 1:1:1:1 ratio to 1 of the 4 study arms at Visit 102 in a double-blind fashion. Assignment to treatment groups will be determined by a computer-generated random sequence using an interactive web-response system (IWRS). The IWRS will be used to assign packages containing double-blind study drug to each subject. Site personnel will confirm that they have located the correct packages by entering a confirmation number found on the package label into the IWRS.

To achieve between-group comparability in Part B, randomization will be stratified by biologic DMARD experience (yes/no), region (Japan versus non-Japan), and disease severity (Disease Activity Score modified to include the 28 diarthrodial joint count [DAS28]-hsCRP ≤ 5.1 versus >5.1). The screening value for hsCRP will be used to calculate DAS28-hsCRP for randomization.

6. A Priori Statistical Methods

6.1. General Statistical Considerations

Statistical analysis of this study will be the responsibility of Eli Lilly and Company or its designee.

This plan describes a priori statistical analyses for safety, efficacy, and health outcomes data that will be performed.

In general, continuous variables will be summarized including number of observations, mean, standard deviation (SD), minimum, median, and maximum values. Categorical variables will be presented as counts and percentages. Data from Part A will be summarized separately from data from Part B. No statistical hypothesis testing is planned for Part A. All tests of treatment effects in Part B will be conducted at the 2-sided α level of .05, unless otherwise stated. No adjustments for multiplicity will be performed.

Unless otherwise specified, statistical analyses to compare treatment groups will use statistical techniques with treatment group and randomization strata [ie, biologic DMARD experience (yes/no), region (Japan versus non-Japan), and baseline DAS28-hsCRP (continuous)] as factors. In addition, for analysis of continuous measures, the baseline value of the dependent variable will be included as a covariate. Fisher's exact test will be used for the analysis of categorical measures unless otherwise specified.

P-values from statistical tests of treatment effects in safety analyses should be interpreted with caution as the analyses are intended to be descriptive and should not be considered as formal hypothesis testing. P-values and confidence intervals (CIs), if reported, provide some evidence of the strength of the finding.

For the purpose of presentation, the treatment groups of Parts A and B will be assigned by randomized treatment, and the treatment groups of Follow-up period will be assigned by the last used treatment.

The analyses for the optional long-term extension is described in Section [6.5.5](#).

Additional exploratory analyses of the data will be conducted as deemed appropriate.

6.1.1. Analysis Population

Unless otherwise specified, efficacy and health outcomes analyses will be conducted on the modified intent-to-treat (mITT) population, defined as all randomized subjects receiving at least 1 dose of study drug. The analysis population (for applicable treatment outcome measures) will be all subjects with both a baseline and at least 1 postbaseline data measurement. Subjects will be grouped according to the randomized treatment. In addition, the primary analyses and key secondary efficacy analyses of Part B will be repeated using the per-protocol set (PPS), defined as all subjects randomly assigned to the study drug and using the study drug for 12 weeks without specified important protocol violations (Section [6.2.2](#)).

Safety analyses will be conducted on the safety population, defined as all randomized subjects receiving at least 1 dose of the study drug and who do not discontinue the study for the reason “Lost to Follow-up” at the first postbaseline visit. Subjects will be grouped according to the randomized treatment.

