Efficacy and health outcomes analyses will be conducted on the modified intent-to-treat population, defined as all randomized subjects receiving at least 1 dose of study drug. Subjects will be grouped according to the randomized treatment. The analysis population (for applicable treatment outcome measures) will be all subjects with both a baseline and at least 1 postbaseline data measurement. Safety analyses will be conducted on the safety population, defined as all randomized subjects receiving at least 1 dose of the study drug. Subjects will be grouped according to the randomized treatment. Data from Part A will be summarized separately from data from Part B. No statistical hypothesis testing is planned for Part A. All tests of treatment effects for Part B will be conducted at the 2-sided α level of .05 unless otherwise stated. No adjustments for multiplicity will be performed.

The primary endpoint in Part B will be analyzed by a logistic regression model with ACR20 at Week 12 as the dependent variable and treatment, biologic disease-modifying antirheumatic drug (DMARD) experience (yes/no), region (Japan vs non-Japan), and baseline DAS28-hsCRP as independent variables. A comparison of each LY3337641 dose to placebo will be presented. Subjects who discontinue from the study earlier than Week 12 and subjects who complete 12 weeks of dosing but do not have sufficient data to derive the ACR20 response will be considered as failing to meet the ACR20.

2. Introduction

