7.1.5. Subjects Lost to Follow-Up

A subject will be considered lost to follow-up if he or she repeatedly fails to return for scheduled visits and cannot be contacted by the study site. Site personnel are expected to make diligent attempts to contact subjects who fail to return for a scheduled visit or are otherwise unavailable for follow-up by the site.

8. Study Assessments and Procedures

Study procedures and their timing (including tolerance limits for timing) are summarized in the Schedule of Activities ([Appendix 2](#)).

A list of the laboratory tests that will be performed for this study is provided in [Appendix 3](#).

Unless otherwise stated in the subsections below, all samples collected for specified laboratory tests will be destroyed within 60 days of receipt of confirmed test results. Certain samples may be retained for a longer period, if necessary, to comply with applicable laws, regulations, or laboratory certification standards.

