8.2.1. Serious Adverse Events

An SAE is any AE from this study that results in one of the following outcomes:

- death
- initial or prolonged inpatient hospitalization
- a life-threatening experience (ie, immediate risk of dying)
- persistent or significant disability/incapacity
- congenital anomaly/birth defect
- considered significant by the investigator for any other reason: important medical events that may not result in death, be life-threatening, or require hospitalization may be considered serious, based upon appropriate medical judgment.

Although all AEs occurring after a subject signs the ICF are recorded in the eCRF, SAE reporting begins after the subject has both signed the ICF and received study drug. However, if an SAE occurs after a subject signs the ICF but prior to receiving study drug, it needs to be reported ONLY if it is considered reasonably possibly related to study procedure.

Study site personnel must alert Lilly or its designee of any SAE within 24 hours of investigator awareness of the event via a sponsor-approved method. If alerts are issued via telephone, they are to be immediately followed with official notification on study-specific SAE forms. This 24-hour notification requirement refers to the initial SAE information and all follow-up SAE information.

Pregnancy (during maternal or paternal exposure to study drug) does not meet the definition of an AE. However, to fulfill regulatory requirements, any pregnancy should be reported following the SAE process to collect data on the outcome for both mother and fetus.

Investigators are not obligated to actively seek AEs or SAEs in subjects once they have discontinued and/or completed the study (the subject's summary eCRF has been completed). However, if the investigator learns of any SAE, including a death, at any time after a subject has been discharged from the study, and he/she considers the event reasonably possibly related to the study drug or study participation, the investigator must promptly notify Lilly.

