8.2.2. Adverse Events of Special Interest

Skin rash is considered an AESI. If a subject develops a rash during the study, the subject should notify the site immediately in order to conduct an unscheduled visit. The visit should be

scheduled as soon as possible to enable evaluation of the rash while it is still present. See Section 8.4.6 for instructions on rash assessment and management.

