8.5. Pharmacokinetics

At the visits and times specified in the Schedule of Activities ([Appendix 2](#)), venous blood samples of approximately 4 mL each will be collected to determine the plasma concentrations of LY3337641. At the baseline visit (Visit 2 in Part A and Visit 102 in Part B), the first dose of study drug will be administered, and subjects will remain at the site and have the PK sample drawn between 30 minutes and 2 hours postdose. At subsequent visits, the PK sample will be drawn at any time during the visit; it is not required that the dose be administered during the visit.

A maximum of 2 PK samples may be drawn at additional time points during the study if warranted and agreed upon between both the investigator and sponsor. For example, if an SAE or a clinically significant rash is observed by the investigator and a PK sample is not scheduled for that visit, a sample may be drawn at that time.

Instructions for the collection and handling of blood samples will be provided by the sponsor. The actual date and time (24-hour clock time) of each sampling will be recorded. It is essential that the actual times of dosing and sampling are recorded accurately.

Drug concentration information that may unblind the study will not be reported to investigative sites or personnel who are blinded to study data.

Plasma samples will be analyzed for LY3337641 at a laboratory approved by the sponsor using validated liquid chromatography-tandem mass spectrometry methodology. Analysis of samples collected from placebo-treated subjects is not planned.

Plasma PK samples may be analyzed for exploratory metabolite identification, as deemed appropriate by the sponsor. The results of such exploratory metabolism work may only be included in the clinical study report (CSR) if deemed appropriate by the sponsor or may be reported in a separate exploratory metabolism report.

Bioanalytical samples collected to measure LY3337641 concentration will be retained for a maximum of 1 year following the last subject visit for the study.

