9.5. Safety Analyses

All safety summaries and analyses will be based on the safety population as defined in Section 9.2.1. Safety will be assessed by evaluating all reported AEs, AESIs, changes in vital signs, and changes in laboratory analytes.

Exposure to each study regimen will be calculated for each subject and summarized for both parts separately by treatment group. Safety analyses will be conducted for both parts separately by treatment group.

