modified intent-to-treat	The intent-to-treat principle asserts that the effect of a treatment policy can be best assessed by evaluating on the basis of the intention to treat a subject (that is, the planned treatment regimen) rather than the actual treatment given. It has the consequence that subjects allocated to a treatment group should be followed up, assessed, and analyzed as members of that group irrespective of their compliance to the planned course of treatment. The modified intent-to-treat population includes all randomized subjects receiving at least 1 dose of study drug. The analysis population (for applicable treatment outcomes measures) will be all subjects with both a baseline and at least 1 postbaseline data measurement.
MTX	methotrexate
per-protocol set	all subjects randomly assigned to the study drug and using the study drug for 12 weeks (ie, the subset of subjects who sufficiently complied with the protocol); results from this population would be likely to exhibit the effects of treatment, according to the underlying scientific model.
PK/PD	pharmacokinetics/pharmacodynamics
qd	once daily
RA	rheumatoid arthritis
SAE	serious adverse event
safety population	all randomized subjects receiving at least 1 dose of the study drug
SAP	statistical analysis plan
screen	the act of determining if an individual meets minimum requirements to become part of a pool of potential candidates for participation in a clinical study
SF-36	Medical Outcomes Study 36-Item Short Form Health Survey
SJC	swollen joint count
study drug	LY3337641 and/or placebo used in the current study
subject	an individual who is or becomes a participant in clinical research, either as a recipient of the investigational product(s) or as a control. A subject may be either a healthy human or a patient.

SUSARs	suspected unexpected serious adverse reactions
TB	tuberculosis
TEAE	treatment-emergent adverse event: any untoward medical occurrence that either occurs or worsens at any time after treatment baseline and that does not necessarily have to have a causal relationship with this treatment
TJC	tender joint count
TST	tuberculin skin test
type I error	rejection of the null hypothesis when it is, in fact, true
ULN	upper limit of normal
VAS	visual analog scale

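### SAP 6.1.1 drops dosed subjects lost to follow-up at the first postbaseline visit from the Part A and Part B safety population; the protocol keeps every dosed subject.

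*SAP*

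**What the plan says.** The protocol gives one definition in three places. The synopsis and section 9.2.1 both state: "Safety analyses will be conducted on the safety population, defined as all randomized subjects receiving at least 1 dose of the study drug". Appendix 1 repeats it as "all randomized subjects receiving at least 1 dose of the study drug". None of the three adds a further condition. Protocol 9.5 then ties the reporting to that set: "All safety summaries and analyses will be based on the safety population as defined in Section 9.2.1".

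SAP 6.1.1 starts from the same definition and adds a condition. Its safety population is "defined as all randomized subjects receiving at least 1 dose of the study drug and who do not discontinue the study for the reason", and the sentence goes on to name loss to follow-up at the first postbaseline visit. SAP 6.4 bases all safety summaries on 6.1.1, for Part A and Part B separately. SAP 6.4.2 makes this population the denominator for adverse event percentages, apart from sex-specific events. The modified intent-to-treat population, also defined in SAP 6.1.1, keeps the subjects that the safety population drops.

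The SAP gives no reason for the added condition, and the change lists for SAP Versions 2 and 3 do not mention it.

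**The concern.** Safety is the primary objective of Part A and part of the primary objective of Part B. The SAP decides who counts for safety partly by what happens after dosing, namely whether and why the subject stopped attending. The protocol has no such rule.

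Two things follow. The denominators of the adverse event and rash percentages, and of the Fisher comparisons in Part B, can differ from those the protocol promises. Also, an event recorded after the first dose in an excluded subject leaves the arm-level tables.

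The rule does not follow the amount of data either. A subject who withdraws consent before the first postbaseline visit, with equally little follow-up, stays in the population.

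**Working it through.** **Who is affected.** The first postbaseline visit is Day 8 ±3 in Part A and Day 15 ±2 in Part B (Protocol Appendix 2). Protocol 7.1.5 counts a subject as lost who "repeatedly fails to return for scheduled visits and cannot be contacted by the study site". The excluded subjects therefore have little or no contact after the first dosing day.

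**Is the exclusion needed to run the analyses?** No. In SAP 6.4.3 the laboratory box plots already require a baseline value and a result at the visit. The shift from normal/high to low requires a dosing-period result, and the full shift table has a missing category. The clause mainly affects summaries to which any dosed subject can contribute, such as adverse events and rash.

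**Can an excluded subject have a recorded post-dose event?** There are three possible routes.

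1. *On-site stay after the first dose.* At the baseline visit, "subjects will remain at the site and have the PK sample drawn between 30 minutes and 2 hours postdose" (Protocol 8.5). An event then falls on Day 1. SAP 6.4.2 uses a case report form flag to separate events before and after the first dose on that day. Protocol 9.5.1 counts events up to the last visit in the dosing period, which for a subject who never returns is Day 1. Such an event is treatment-emergent under both documents and would be dropped. This route is clear.
2. *Unscheduled rash visit.* Protocol 8.2.2 says: "If a subject develops a rash during the study, the subject should notify the site immediately in order to conduct an unscheduled visit". SAP 6.1.1 does not say whether its first postbaseline visit means the first scheduled one. If an unscheduled visit counts, the subject stays in; if not, the subject is out. This route is ambiguous.
3. *SAE learned of remotely.* Protocol 8.2.1 says "SAE reporting begins after the subject has both signed the ICF and received study drug", so a later report is possible. Under Protocol 9.5.1, however, an event after the last attended dosing-period visit may not be a TEAE at all. This route is doubtful.

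**Size.** Arm sizes come from Protocol 9.1: 32/4 = 8 in Part A and 244/4 = 61 in Part B. The documents give no event rates or loss rates, so the event counts and losses below are assumed. With N dosed, x with the event, k excluded and j of those k having the event, the percentage goes from x/N to (x − j)/(N − k).

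| Assumed arm | k | All excluded had the event (j = k) | None had it (j = 0) |
|---|---|---|---|
| Part A, 1/8 = 12.5% | 1 | 0/7 = 0% | 1/7 = 14.3% |
| Part B, 5/61 = 8.2% | 1 | 4/60 = 6.7% | 5/60 = 8.3% |
| Part B, 5/61 = 8.2% | 2 | 3/59 = 5.1% | 5/59 = 8.5% |
| Part B, 5/61 = 8.2% | 3 | 2/58 = 3.4% | 5/58 = 8.6% |

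One exclusion removes 1/8 = 12.5% of a Part A arm and 1/61 = 1.6% of a Part B arm; three remove 3/61 = 4.9% of a Part B arm.

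The plan has no figure of its own on this point. Its only computable design figure is the power for ACR20 (at least 80% with 61 per arm, 30% versus 55%). It reproduces at 80.5% and is not affected.

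**The case against.** The strongest reply is that the clause touches almost nobody and hides nothing. A subject lost this early contributes little data, so restoring such subjects mostly adds event-free people to the denominator. Individual events remain visible: SAP 6.4.2 lists all adverse events, SAP 6.2.1 lists disposition for all screened subjects, the DSUR dataset holds all randomized subjects (SAP 6.5.3), and the registry analysis counts SAEs whether or not they are treatment-emergent (SAP 6.5.4). Safety reviews continue during the study (Protocol 8.4.7). No testing is planned in Part A, and safety p-values are descriptive (SAP 6.1). All of this stands and limits the size of the point. It does not explain why the SAP departs from the protocol, and a listing does not correct an arm-level percentage.

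A second reply is that Protocol 9.2 lets a method change that is not a principal feature be justified in the clinical study report. That also stands. A reader might infer that a protocol amendment is missing; the documents do not support this. The issue is the changed population and the absent reason.

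Third, different Ns in the baseline tables (modified intent-to-treat) and the safety tables are an ordinary result of having two populations and are not a defect in themselves.

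**Conclusion.** The point holds as an unexplained conflict between SAP 6.1.1 and the protocol's safety population, applied to all Part A and Part B safety summaries. It changes adverse event denominators and can drop a recorded event, with the stay after the first dose as the one clear route. The numbers rest on assumed event counts and losses; the true number affected may be zero. The Part A case of 1/8 becoming 0/7 needs the lost subject to hold the arm's only event. Efficacy sample size and power do not change.

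Three stronger readings are tempting and should not be drawn. One is that rashes and SAEs will certainly vanish from the tables: the rash route is ambiguous, and a late SAE may not be a TEAE in any case. Another is that the clause favours the drug: the percentage can move either way in any arm, including placebo. The third is that the clause was added after Part A results were seen: nothing in the SAP shows when it was introduced.

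**What to change.** In SAP 6.1.1, delete the lost-to-follow-up condition so that the safety population is "all randomized subjects receiving at least 1 dose of the study drug", as in the protocol. If the exclusion is wanted, keep it as a sensitivity analysis only. Report by arm the number of dosed subjects lost to follow-up at the first postbaseline visit.

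Part B enrols only after the Part A interim, and SAP 6.6 has the study team unblinded to Part A results. An edit to the current SAP version therefore comes after Part A unblinding. Record for Part A that the change restores the protocol definition and was not chosen in light of the data.

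The cost is one deleted clause, one count per arm and a short note. The small downside is that a few subjects with little follow-up enter the denominators, mostly as event-free.

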6.1.2. Baseline Definition

The baseline will be defined as the last available value before the first administration of study drug for both efficacy analyses, including unscheduled measurements for both parts separately. In most cases, this will be the measure recorded on Study Day 1 (Visit 2 in Part A and Visit 102 in Part B). Change from baseline values will be calculated as the postbaseline value minus the baseline value for each scheduled postbaseline time point. If the baseline value is missing (ie, no screening values, no Day 1 value, and no unscheduled measurements), the change from baseline will be missing as well.

For safety analyses, the baseline includes all pre-existing conditions recorded and any adverse events (AE) recorded before the first dose of study drug. Detailed definitions for each period of the studies are described in Section 6.4.2.

